In a cross-sectional analysis of European Caucasian men and women, we found that  $\text{Na}^+$  storage in muscle and skin increases with age, is more pronounced in men than in women, and is associated with higher blood pressure, while tissue water remains constant at all ages. This state-of-affairs leads us to the hypothesis that tissue  $\text{Na}^+$  storage characterizes a disruption of internal environment composition, which may be causally linked to primary hypertension and insulin resistance. The increase in tissue  $\text{Na}^+$  content we observed is similar to the age-dependent increase in blood pressure and pulse wave velocity reported by Vaitkevicius et al. 20 years ago (**Fig. 5 A&B**). Because our preliminary data suggest a strong association between age-dependent tissue accumulation and blood pressure levels, we hypothesize that successful prevention of age-dependent increases in tissue  $\text{Na}^+$  content will lower blood pressure, reduce inflammation, improve insulin sensitivity, and will reduce cardiovascular risk long-term. To address this hypothesis, we have initiated a prospective, independent study in European Caucasian men and women across age ranges with careful measurements of skin  $\text{Na}^+$  content with NaMRI (**Fig. 5C**). This second (unpublished) study confirms the age-related and sex-related effects. The relationship between NaMRI measured tissue  $\text{Na}^+$  stores and blood pressure suggests that increases in skin  $\text{Na}^+$  content account for 50% of the blood pressure increase in men and somewhat less (where we have fewer data) in women. Our overarching hypothesis is that by flattening the time course of tissue  $\text{Na}^+$  storage with age, we will improve healthspan and thereby prevent cardiovascular disease (Fig. 5D).

[figure not shown]

Fig. 5. Panels A – B: Relationship between age and blood pressure and pulse-wave velocity. (Adapted from Vaitkevicius et al.). Our preliminary data show similar age-dependent increases in skin Na+ storage in Caucasians (Panel C). These preliminary findings result in the hypothesis that attenuation of Na+ storage with age may prevent CVD (Panel D).

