missing link towards a new and better understanding of the chronic pro-inflammatory state that leads to cardiovascular disease with aging (Fig. 1). Similarly, Na+ stored in muscle may predispose to energy deficit and insulin resistance. Tissue Na+ storage thus may not only be pathophysiologically linked to arterial hypertension, but also with diabetes mellitus, another highly relevant cardiovascular risk factor. Successful therapeutic bending of the slope relationship between age and tissue Na+ accumulation (Fig. 1) therefore promises to become a novel, important approach for cardiovascular disease prevention.

In this clinical project, we will take the first step towards therapeutic “bending” of the age/Na+ accumulation relationship to a flatter slope (Fig. 2). We will establish a cohort of 200 subjects with pre-hypertension, age: 30 to 80 years. The cohort will be controlled for

gender, race, and age so that cross-sectional analysis of the cohort characteristics will provide us with new information on the effect of race on tissue Na+ content (Aim 1, Fig. 2). In a prospective, double-blinded randomized-controlled trial, we then will test the hypothesis that 8 weeks of a reduced salt diet or drug treatment with either the MR antagonist spironolactone, or with the diuretic hydrochlorothiazide, will reduce skin and muscle Na+ content (Aim 2, short-term longitudinal readout, Fig. 2). Tissue Na+ content will be our primary endpoint in Aims 1 and 2. As secondary endpoints, we will read out differences in blood pressure, skin forearm blood flow by BOLD MRI, and arterial stiffness by measurement of pulse wave velocity. Finally, we speculate that lower tissue Na+ content reduces a pro-inflammatory immune cell phenotype and improves insulin sensitivity (Aims 3 and 4). We will address the following specific aims:

- Specific Aim 1:** To test the hypothesis that African Americans are characterized by increased tissue Na+ storage, which is paralleled by higher blood pressure, reduced forearm blood flow, and enhanced pulse wave velocity
- Specific Aim 2:** To test the hypothesis that treatment with spironolactone reduces tissue Na+ content (Primary Outcome)
- Specific Aim 3:** To test the hypothesis that Na+ storage leads to immune cell activation (Secondary Outcome)

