## 10.0 Statistical Considerations

**Power and sample size calculations:** For Aim 1, 100 per race group (200 in total) provides 85% power to detect an effect size of 0.42 in blood pressure, forearm blood flow or PWV with two-sided type I error = 5%. For Aim 2, assuming a reduction in muscle Na+ of 5 mmol/L and SD=6.0 mmol/L by drug treatment, 85% power and Bonferroni adjusted 2-sided type I error (significant level) test at level 1%, a sample size of 41 subjects per group (161 in total) is needed. For Aim 3, the proposed sample size 200 enable us to detect the Pearson Correlation of 0.21 or higher (absolute value) between Na+ storage change and immune cell activity change with two-sided type I error = 5%. For Aim 4, the sample size calculation is the same as Aim 3.

**Data collection and analysis:** For Aim 1, summary statistics of blood pressure, forearm blood flow and PWV at week 0 will be provided for both African American group and Caucasian group. We will test the difference of these variables among two race group using two sample t-test. For Aim 2, we will conduct univariate analysis for comparing the magnitude of the Na+ tissue content among each pair of treatment groups using two sample t-test, and the Bonferroni correction will be applied to control the type I error due to multiple comparisons. In addition, partial linear model will be used to estimate the linear treatment effect and interaction effect while adjusting the nonlinear effect such as age and gender. For Aim 3, we will calculate the Pearson correlation of Na+ storage change (before and after treatment) and the immune cell activity change. Alternatively, Spearman correlation or Kendall's tau will be calculated to capture the nonlinear correlation. We will also perform linear regression with all covariates and pairwise interactions in the model to adjust the impact of factors such as age, sex, and body weight on tissue sodium. For Aim 4, we focus on the association between tissue sodium change and insulin sensitivity change using the same analysis methods as in Aim 3.

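### Aim 2's first-listed test ignores baseline tissue Na+ and leaves the outcome undefined; a prespecified ANCOVA would gain precision from data already collected

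*Combined protocol and SAP*

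**What the plan says.** Section 2.0 makes tissue Na+ content the primary outcome of Aim 2. In Section 10.0 the first analysis listed for Aim 2 compares the size of "tissue content among each pair of treatment groups using two sample t-test, and the Bonferroni correction will be applied". No covariate enters this test. A partial linear model is then added, "adjusting the nonlinear effect such as age and gender". It names neither Week 0 Na+ nor race, and neither analysis is designated as the main one.

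The sample size assumes a reduction in muscle Na+ "of 5 mmol/L and SD=6.0 mmol/L by drug treatment", with 85% power at a Bonferroni-adjusted two-sided 1% level and 41 subjects per group. The plan does not say whether the outcome is the Week 8 value or the change, or which of them the SD describes. Two phrases lean towards change: the power text speaks of a reduction, and Section 2.0 describes a "Aim 2, short-term longitudinal readout, Fig. 2". Section 10.0 uses the word change outright only for Aims 3 and 4, for example "storage change (before and after treatment) and the immune cell activity change".

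The baseline data are already planned. Section 6.0 and the Schedule of Procedures place the sodium MRI at Week 0 and Week 8, and treatment starts only after the second baseline visit. Section 5.0 stratifies randomisation by gender and race.

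**The concern.** A covariate-free t-test on a continuous outcome with a pre-treatment measurement of the same quantity leaves variance in the comparison that could be removed without further data. The protocol itself expects its stratification factors to matter for Na+ levels. Section 1.0 reports that Na+ "storage in muscle and skin increases with age, is more pronounced in men than in women", and Aim 1 is "To test the hypothesis that African Americans are characterized by increased tissue" Na+ storage. Ignoring the strata makes the t-test conservative to the extent that gender and race predict the tested quantity. The documents support this for levels, but not for change.

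Because the outcome is undefined, someone must later choose between Week 8 values and change, and the power depends on that choice. ANCOVA deals with both problems. It is more precise than either t-test, and its treatment contrast is the same whichever way the outcome is written.

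**Working it through.** **Inputs.** From Section 10.0: difference 5 mmol/L, SD 6.0 mmol/L, 85% power, two-sided 1%, 41 per group. Four arms give six pairs, so an exact Bonferroni level is 0.05/6 = 0.0083. The documents do not give the correlation ρ between Week 0 and Week 8 Na+. I assume 0.3 to 0.8, with equal variances at both visits and no dropout.

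**Reproducing the plan.** An unadjusted two-sample t-test (noncentral t, df = 2n − 2) needs 39.3, so 40 per group, at 1%, and 40.7, so 41 per group, at 0.05/6. Power at 41 per group is 86.8% and 85.4% respectively. The planned size therefore takes no credit for baseline adjustment. I use 0.05/6 below because it returns 41 exactly, and give the stated 1% level alongside.

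**Variance of an arm difference**, with σ the SD at one visit and n per arm:
- t-test on Week 8 values: 2σ²/n
- t-test on change: 2 × 2σ²(1 − ρ)/n
- ANCOVA on Week 0: 2σ²(1 − ρ²)/n

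ANCOVA relative to the change test is (1 − ρ²)/[2(1 − ρ)] = (1 + ρ)/2, which is 0.65 at ρ = 0.3 and 0.90 at ρ = 0.8. ANCOVA relative to the Week 8 test is 1 − ρ², which is 0.91 and 0.36. So the variance falls by 35% to 10%, or by 9% to 64%. Both ratios are below 1 for every ρ strictly between 0 and 1.

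**Effective SDs.**
- (a) If 6.0 is the Week 8 SD, the ANCOVA residual SD is 6√(1 − ρ²): 5.72 at ρ = 0.3, 5.20 at 0.5, 3.60 at 0.8. The SD of change is 6√[2(1 − ρ)]: 7.10, 6.00, 3.79.
- (b) If 6.0 is the SD of change, the Week 8 SD is 6/√[2(1 − ρ)]: 5.07, 6.00, 9.49. The ANCOVA residual SD is 6√[(1 + ρ)/2]: 4.84, 5.20, 5.69.

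**Power at 41 per group, alpha 0.05/6** (matched t-test: 85.4% throughout):

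| ρ | ANCOVA (a) | ANCOVA (b) | t-test: 6.0 is SD of change, Week 8 tested | t-test: 6.0 is Week 8 SD, change tested |
|---|---|---|---|---|
| 0.3 | 89.1% | 97.4% | 95.8% | 68.5% |
| 0.4 | 91.8% | 96.2% | 92.0% | 76.8% |
| 0.5 | 94.8% | 94.8% | 85.4% | 85.4% |
| 0.6 | 97.6% | 93.2% | 74.6% | 93.2% |
| 0.7 | 99.4% | 91.4% | 58.7% | 98.3% |
| 0.8 | >99.9% | 89.5% | 38.1% | 99.9% |

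At the stated 1% level, ANCOVA runs from 90.3% to over 99.9% under (a) and from 97.8% down to 90.6% under (b). The lowest mismatched powers become 40.6% and 70.8%.

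**Subjects per group for 85% power at 0.05/6**, in the order of the table rows: (a) 38, 35, 31, 27, 22, 16; (b) 28, 30, 31, 33, 35, 37; against 41 for the matched t-test.

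**Check of the formulas.** Simulating the full four-arm model with Week 0 Na+, gender, race and age (4,000 runs, 41 per group, alpha 0.05/6) gave 89.3%, 95.1% and 99.98% under (a) and 97.9%, 95.0% and 89.7% under (b), at ρ = 0.3, 0.5 and 0.8.

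**If more are randomised.** For Aim 3 the plan states that "the proposed sample size 200 enable us to detect the Pearson Correlation of 0.21 or higher" between changes, which suggests that all 200 might be treated. Section 5.0 also enrols subjects who stop at Week 0, and the allocation ratio is not stated. With 200/4 = 50 per arm, the matched t-test has 92.7% at 0.05/6 (93.6% at 1%). ANCOVA at 0.05/6 has 95.1% to over 99.9% under (a), or 99.3% down to 95.3% under (b).

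**The case against.** The strongest reply is that the wording favours change for both the outcome and the SD. On that reading the t-test already exceeds its 85% target, and the gain shrinks as ρ rises: ANCOVA has 89.5% at ρ = 0.8 and 87.5% at 0.9. The largest gains need the less favoured reading, and the lowest t-test powers need a mismatch that the text does not suggest and that can also raise power. This stands. It limits the size of the gain but not its direction. The mismatch figures show why a definition is needed; they are not the plan's expected power.

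Secondly, an adjusted model is already planned, and its covariate list is open-ended. That is true, but an open list does not prespecify Week 0 Na+, and the Bonferroni correction is attached to the t-tests.

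Thirdly, one four-arm model pools the residual variance. If the arms differ in spread, a contrast between the two most variable arms can exceed its nominal 0.83%. With assumed arm SDs of 7, 7, 6, 5 or 8, 8, 5, 5, simulation gives error rates of roughly 1.6% to 2.8%, while the pairwise t-test stays near nominal. This is a fair caution. It depends on unequal spread, which the documents neither show nor exclude, and robust standard errors or ANCOVA within each pair remove it.

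Finally, Section 6.0 describes randomisation before the Week 0 measurements, and the diet arm is unblinded. Treatment nonetheless starts after the second baseline visit, so Week 0 Na+ is a pre-treatment covariate, and a change score would carry the same caveat.

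**Conclusion.** The concern holds as an improvement that needs no new data; it is not a flaw in validity. The first-listed Aim 2 test is unbiased and has 85.4% power at 0.05/6 if SD 6.0 describes what is tested. ANCOVA on Week 0 Na+ raises this to at least 89.1% over the assumed range of ρ, and to 94.8% at ρ = 0.5 on either reading of the SD. The size of the gain rests on ρ, which the documents do not give, and on equal variances at the two visits. Against a change-score test it is modest when ρ is high (10% of variance at 0.8). Any further gain from gender, race and age cannot be sized from the documents. The missing definition of the outcome and its SD is a gap in its own right and should be closed whichever test leads.

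**What to change.** In Section 10.0:

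1. Make the main Aim 2 analysis one ANCOVA of Week 8 tissue Na+ on arm, Week 0 Na+ of the same tissue, gender, race and age, with the Bonferroni-corrected pairwise contrasts taken from it.
2. Specify robust standard errors, or fit the ANCOVA within each pair of arms, to guard against unequal spread.
3. Keep the t-test as a supporting analysis, and state whether it uses Week 8 values or change.
4. State which of these the SD of 6.0 mmol/L describes.

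The cost is wording only: no new visits, scans or subjects, and a few degrees of freedom for the covariates. The model uses subjects with both scans, as a change-score test also would.

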## 5.0 Enrollment/Randomization

The study will be conducted at the Vanderbilt University Medical Center. Institutional Review Board approval and written informed consent will be obtained from all study subjects.

We propose to study a total of 200 subjects controlled for race (50% African Americans, 50% Caucasians) and gender (50% female, 50% male). Subjects will be recruited from the Outpatient Clinics at VUMC (including the General Medicine Clinic and the Hypertension Clinic), as well as by emails, flyers, and other recruitment tools. All participants will have a baseline assessment, as well as on-going monitoring, of their health status as documented in their medical record.

[figure not shown]
Subjects will be randomly assigned to one of the study arms (diet, spironolactone, chlorthalidone, or placebo). Randomization will be determined using a stratified permuted-block randomization method. Stratification will be based on gender and race.

One treating physician will be unblinded as to whether subjects are receiving spironolactone or chlorthalidone and will guide decisions regarding subjects who develop abnormal serum potassium levels.

To specifically address Aims 1, 3 and 4, we will also enroll subjects who will only complete visits through Week 0. In addition, to aid data analysis, we will also re-enroll subjects who will complete a follow-up visit consisting of a blood draw.

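### Aim 2's single-step Bonferroni over six pairwise tests is valid and meets its 85% power, but a Holm/Shaffer step-down test would give more power at the same 5% family-wise error

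*Combined protocol and SAP*

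**What the plan says.** Section 5.0 sets up four arms: "Subjects will be randomly assigned to one of the study arms (diet, spironolactone, chlorthalidone, or placebo". For Aim 2, section 10.0 (data collection and analysis) compares tissue sodium "among each pair of treatment groups using two sample t-test", and then states that "the Bonferroni correction will be applied to control the type I error due to multiple comparisons". Neither section names a step-down method.

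The sample-size paragraph of section 10.0 builds the correction in. It takes a reduction in muscle sodium "of 5 mmol/L and SD=6.0 mmol/L by drug treatment" and specifies "85% power and Bonferroni adjusted 2-sided type I error", with the level printed as 1%. From this it concludes that "a sample size of 41 subjects per group (161 in total) is needed". Section 5.0 plans a larger enrolment: "We propose to study a total of 200 subjects controlled for race". Section 2.0 labels Aim 2 the primary outcome and states its hypothesis for spironolactone. Section 8.0 plans no interim analysis, so no alpha is spent elsewhere.

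**The concern.** Single-step Bonferroni holds all six p-values to 0.05/6, even after some hypotheses have been rejected. Holm's procedure relaxes the threshold after each rejection. It keeps strong family-wise control with no extra assumption about dependence.

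All-pairs testing of four means allows a further step. The number of true equalities can only be 6, 3, 2, 1 or 0. Once one pair differs, at most three of the others can still be equal, so Shaffer's divisors 6, 3, 3, 3, 2, 1 are valid.

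At stake is some power on the primary endpoint. The effect is greatest for contrasts smaller than the 5 mmol/L that the plan assumes for the drugs. In a trial where each subject has two MRI scans and two clamp studies, power that needs no extra subjects is worth having.

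**Working it through.** **Inputs.** From section 10.0: difference 5 mmol/L, SD 6.0 mmol/L, 41 per group, 85% power, Bonferroni adjustment, two-sided t-tests. From section 5.0: four arms, hence 4 × 3 / 2 = 6 pairs. Family-wise level 5%.

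**Step 1: reproduce the plan's 41.** The normal formula is n = 2(z₁₋α/₂ + z₀.₈₅)² SD² / difference².
- α = 0.05/6 = 0.0083: 2 × (2.638 + 1.036)² × 36/25 = 38.9, so 39; the exact t calculation gives 41.
- α = 0.01: 2 × (2.576 + 1.036)² × 36/25 = 37.6, so 38; the exact t calculation gives 40.

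At n = 41 the noncentrality is 5 / (6√(2/41)) = 3.77 on 80 degrees of freedom. Power is 85.4% at 0.05/6 and 86.8% at 0.01. The stated 41 therefore matches 0.05/6, and the printed 1% is probably a rounding of 0.83%. (4 × 41 is 164, not 161; this does not affect the point.)

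**Step 2: compare procedures.** 200,000 simulated four-arm trials per scenario, pairwise t-tests, SD 6. Divisors are 6 throughout (Bonferroni); 6, 5, 4, 3, 2, 1 (Holm); 6, 3, 3, 3, 2, 1 (Shaffer). Effects are changes in mmol/L relative to placebo. The plan gives 5 mmol/L for drug treatment only, so all diet effects and the graded pattern are assumptions.

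| Scenario, 41 per arm | Contrast | Bonferroni | Holm | Shaffer |
|---|---|---|---|---|
| Spironolactone only, −5 | spironolactone v placebo | 85.5% | 87.8% | 89.9% |
| Both drugs −5 | drug v placebo | 85.4% | 89.3% | 90.3% |
| All three active arms −5 | each v placebo | 85.4% | 87.8% | 89.9% |
| Drugs −5, diet −2.5 | drug v placebo | 85.4% | 87.1% | 89.2% |
| Drugs −5, diet −2.5 | diet v placebo | 21.5% | 27.1% | 29.9% |
| Diet −2, chlorthalidone −3, spironolactone −5 | spironolactone v placebo | 85.3% | 85.9% | 86.8% |

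- In the first three rows the gain is 2.3 to 4.0 points (Holm) and 4.4 to 5.0 points (Shaffer).
- For the diet contrast it is 27.1 − 21.5 = 5.6 and 29.9 − 21.5 = 8.4 points.
- In the graded row it is 0.6 and 1.5 points.

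**Step 3: 50 per arm.** This assumes that all 200 are randomised equally and remain evaluable. For 5 mmol/L contrasts Bonferroni gives 92.7%, Holm 94.2% to 95.3% and Shaffer 95.4% to 95.7%. The gain is about 1.5 to 3 points.

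**Step 4: what does not change.** The first step uses 0.05/6 under all three rules, so the chance of detecting at least one true difference is identical (for example 97.1% with spironolactone only, n = 41). Simulated family-wise error stayed at or below about 4.5% in every scenario.

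**Step 5: in subjects.** Bonferroni needs 46 per arm for 90.0% power, about what Shaffer gives at 41 (89.9%) when spironolactone alone works. The difference is 5 per arm, or 20 in all.

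**The case against.** The strongest reply is that nothing here is wrong. Bonferroni is valid and pre-specified, and the sample size already pays for it: 85.4% against a target of 85%, and 92.7% if 50 per arm are analysed. That stands. A reader might infer that the primary analysis is underpowered or faulty; the documents do not support this.

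A reader might also take 2 to 5 points as a general loss. It is not. It holds at 41 per arm with all real differences at 5 mmol/L and 0.05/6 as the baseline. Against a literal 1% level (86.9% simulated), with spironolactone alone effective, the gain is 87.8 − 86.9 = 0.9 points (Holm) or 89.9 − 86.9 = 3.0 points (Shaffer). The larger gains for diet rest on an effect that the plan does not state.

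Nor is the loss without any return. Single-step Bonferroni has simple matching simultaneous intervals, and step-down tests do not. In simulation at n = 41, Shaffer rejected at least one contrast whose Bonferroni interval included zero in about 15% of trials (spironolactone only, or all three arms at −5) and about 29% with diet at −2.5. This is a real cost, although section 10.0 promises no simultaneous intervals.

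Finally, the family itself is unsettled. Tissue sodium covers skin and muscle, and the plan does not say whether both enter the correction. Defining the family can matter more than the procedure: spironolactone versus placebo tested alone at 5% would have about 96% power at n = 41. But the ambiguity applies equally to the present sentence, so it shapes the fix and does not defeat it.

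The surplus enrolment does not dispose of the point either. Section 5.0 also enrols subjects who stop at week 0, and section 10.0 states no dropout allowance, so 50 evaluable per arm is not assured.

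**Conclusion.** The point holds as an optional, low-cost efficiency gain. For the six-test family that the plan describes, a step-down procedure is never worse than single-step Bonferroni and is sometimes better, at the same 5% family-wise error. Under the plan's own effect and SD at 41 per arm, it is worth about 2 to 4 points per contrast (Holm) or 4.5 to 5 points (Shaffer). The gain shrinks with more subjects or when the other effects are smaller than the one being tested, grows for weaker interventions, and is nil for finding at least one difference. These figures assume normal outcomes, equal SDs, equal allocation and one tissue.

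**What to change.** Replace the Bonferroni sentence in section 10.0 with:

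> Within each declared family of six pairwise tests, p-values are tested by Holm's step-down procedure with Shaffer's divisors (0.05/6, 0.05/3, 0.05/3, 0.05/3, 0.05/2, 0.05). If skin and muscle sodium are both confirmatory, 0.05 is first split between them. The step-down test governs significance; Bonferroni intervals are descriptive.

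State before unblinding whether one tissue or both are confirmatory. Writing out the thresholds also removes the doubt over the printed 1%.

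For a single family, 41 per group can stay as a conservative size. It is not conservative if alpha is split equally: at 0.025/6 = 0.0042, the calculation in Step 1 gives 79.1% for a 5 mmol/L muscle contrast under Bonferroni, so the size would need to be looked at again.

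The cost is a short text change and no extra subjects. The downside is that some step-down rejections will have a Bonferroni interval that includes zero, which is why the text must say which result governs.
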